## **8.0                   Handling of Potential Intercurrent Events for the Primary and Key Secondary Endpoints**

Not applicable.

## **9.0                   Effectiveness Analyses**

### **9.1                   General Considerations**

All effectiveness analyses will be conducted in the Evaluable Population 1, 2, 3 and 4. Baseline for effectiveness is defined as the last non-missing effectiveness assessment before the first Coolsculpting procedure. All Confidence Intervals (CIs) will be 2-sided 95% CIs, unless stated otherwise.

The summaries will be provided by participants with 1 treatment session, participants with 2 treatment sessions and overall, where applicable.

### **9.2                   Handling of Missing Data**

No imputation of missing data will be made for any effectiveness analysis.

### **9.3                   Primary Effectiveness Endpoint(s) and Analyses**

#### **9.3.1               Primary Effectiveness Endpoint(s)**

The primary effectiveness endpoint of this study is the proportion of participants with “satisfied” or “very satisfied” on the Item 1 for the CSQ-Midsection, measured at Week 12 (Visit 8) for participants who receive 1 treatment session, or at Week 20 (Visit 9) for participants who receive 2 treatment sessions, or at 12 weeks +14 days post treatment

---

session 2 for participants who had their treatment session 2 rescheduled because of the CoolSculpting® Elite treatment hold in the US on / after 24th August 2021.

### **9.3.2 Main Analysis of Primary Effectiveness Endpoint(s)**

The CSQ consists of 6 versions: CSQ-Midsection, CSQ-Overall, CSQ-Upper Arms, CSQ-Inner Thighs, CSQ-Outer Thighs, CSQ-Fat under chin. However, only CSQ-Midsection will be used for the primary analysis. In each version, the CSQ Item 1 is about rating the participant overall satisfaction with the results of the fat reduction procedure on the treated body area based on the following categories:

- Very satisfied
- Satisfied
- Neither satisfied nor dissatisfied
- Dissatisfied
- Very dissatisfied

The number and percentage of participants with “satisfied” or “very satisfied” on the Item 1 for the CSQ-Midsection at Week 12 (Visit 8) for participants who receive 1 treatment session, or at Week 20 (Visit 9) for participants who receive 2 treatment sessions, or at 12 weeks +14 days post treatment session 2 for participants who had their treatment session 2 rescheduled because of the CoolSculpting® Elite treatment hold in the US on / after 24th August 2021 will be summarized for the Evaluable Population 1 and the two-sided Fisher’s exact 95% CI on the percentage will be provided.

A listing will be provided for CSQ-Midsection for the Safety Population.

### **9.3.3 Sensitivity and Supplementary Analyses of the Primary Effectiveness Endpoint(s)**

Not applicable.

## **9.4 Secondary Effectiveness Endpoints and Analyses**

### **9.4.1 Key Secondary Effectiveness Endpoints**

The key secondary effectiveness endpoints include:

- The proportion of participants who received treatment to abdomen and flank and one or more additional body areas for treatment with “satisfied” or “very satisfied” on CSQ-Overall Item 1 measured at Week 12 (Visit 8, 12-week follow-up) for participants who receive only 1 treatment session to all treated body areas, or at Week 20 (Visit 9, 12-week follow-up) for participants who receive 2 treatment sessions to any or all treated body areas, or at 12 weeks +14 days post treatment session 2 for participants who had their treatment session 2 rescheduled because of the CoolSculpting® Elite treatment hold in the US on / after 24th August 2021.
- The proportion of participants with “satisfied” or “very satisfied” on individual treated body area (upper arms, inner thighs, outer thighs, fat under chin) CSQ Item 1 measured at Week 12 (Visit 8, 12-week follow-up) for participants who receive only 1 treatment session, or at Week 20 (Visit 9, 12-week follow-up) for participants who receive 2 treatment sessions for the respective treated body areas, or at 12 weeks +14 days post treatment session 2 for participants who had their treatment session 2 rescheduled because of the CoolSculpting® Elite treatment hold in the US on / after 24th August 2021.
- Correct identification of baseline vs 12-week post-final treatment images of the treated body area(s) by at least two out of three blinded, independent reviewers for the following body areas:
  - Midsection
  - Upper arms
  - Inner thighs
  - Outer thighs
  - Submental area

Success will be defined as at least 70% correct identification of the pre-treatment images.

#### 9.4.2 Main Analyses of Key Secondary Effectiveness Endpoints

The number and percentage of participants with “satisfied” or “very satisfied” on the Item 1 for the CSQ-Overall, CSQ-Upper Arms, CSQ-Inner Thighs, CSQ-Outer Thighs and CSQ-Fat Under Chin, at Week 12 (Visit 8) for participants who receive 1 treatment session, or at Week 20 (Visit 9) for participants who receive 2 treatment sessions, or at 12 weeks +14 days post treatment session 2 for participants who had their treatment session 2 rescheduled because of the CoolSculpting® Elite treatment hold in the US on / after 24th August 2021 will be summarized for the Evaluable Population 4 (overall) and Evaluable

Population 2 (other treated body areas) and the two-sided Fisher's exact 95% CI on the percentage will be provided.

The number and percentage of participants with correct identification of baseline vs 12-week post-final treatment by 2/3 and 3/3 blinded, independent reviewers for the following body areas will be summarized for the Evaluable Population 1 (midsection) and Evaluable Population 2 (other treated body areas) and the two-sided Fisher's exact 95% CI on the percentage will be provided:

- Midsection
- Upper arms
- Inner thighs
- Outer thighs
- Submental area

Listings will be provided for CSQ-Overall, CSQ-Upper Arms, CSQ-Inner Thighs, CSQ-Outer Thighs and CSQ-Fat Under Chin, and correct identification of baseline vs 12-week post-final treatment for the Safety Population.

### 9.4.3 Sensitivity and Supplementary Analyses for Key Secondary Effectiveness Endpoints

Not applicable.

[figure not shown]
#### 9.4.4 Supportive Secondary Effectiveness Endpoints and Analyses

Not applicable.

## 9.5 Exploratory Effectiveness Endpoints and Analyses

### 9.5.1 Exploratory Effectiveness Endpoints

The exploratory effectiveness endpoints include:

•  [REDACTED]

- [REDACTED]
- | [REDACTED]
- | [REDACTED]
- | [REDACTED]
- | [REDACTED]
- [REDACTED]
- [REDACTED]
- [REDACTED]
- | [REDACTED]
- | [REDACTED]
- | [REDACTED]
- | [REDACTED]
- [REDACTED]

#### 9.5.2

#### Main Analysis of Exploratory Efficacy Endpoints

- [REDACTED]
- [REDACTED]

[REDACTED]

In addition, two-sided 95% CI on mean change from baseline by visit will be calculated based on the paired t-test. P-value on change from baseline by visit will be provided based on the paired t-test.

The number and percentage of participants in each category for each item of CGPQ at Week 12 (Visit 8) for participants who receive 1 treatment session, or at Week 20 (Visit 9) for participants who receive 2 treatment sessions, or at 12 weeks +14 days post treatment session 2 for participants who had their treatment session 2 rescheduled because of the CoolSculpting® Elite treatment hold in the US on / after 24th August 2021 will be summarized for the Evaluable Population 1 and Evaluable Population 4.

The number and percentage of participants in each category of CSQ-Midsection Item 2 at Week 12 (Visit 8) for participants who receive 1 treatment session, or at Week 20 (Visit 9) for participants who receive 2 treatment sessions, or at 12 weeks +14 days post treatment session 2 for participants who had their treatment session 2 rescheduled because of the CoolSculpting® Elite treatment hold in the US on / after 24th August 2021 will be summarized for the Evaluable Population 1 and the two-sided Fisher's exact 95% CI on the percentage of participants with improvement (a lot of improvement, moderate improvement, and a little improvement) will be provided.

The number and percentage of participants reporting noticeable improvement in any treated body area, all treated body areas, and each treated body area at Week 4 (Visit 4) post treatment session 1 will be summarized for the Evaluable Population 1 (midsection) and Evaluable Population 2 (other treated body areas) and Evaluable Population 3 (any treated body area, all treated body areas) and the two-sided Fisher's exact 95% CI on the percentage will be provided.

For midsection, the descriptive statistics of the adjusted total volume of fat (cc) at baseline and post-baseline visits, [REDACTED]

[REDACTED]

For outer thigh (left, right, and combined left and right) and submental area, the descriptive statistics of the volume of fat (cc) change from baseline values will be provided for the Evaluable Population 2.

The number and percentage of participants with correct identification of baseline vs. 4-week post treatment session 1 by 2/3 and 3/3 blinded, independent reviewers for the following body areas will be summarized for the Evaluable Population 1 (midsection) and Evaluable Population 2 (other treated body areas) and the two-sided Fisher's exact 95% CI on the percentage will be provided:

- Midsection
- Upper arms
- Inner thighs
- Outer thighs
- Submental area

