### 7.1. Discontinuation of Study Intervention

During the treatment, study intervention may be discontinued due to significant discomfort, wellness issues, psychological issues, or the participant's refusal to continue the treatment.

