#### 8.1.1. Patient-reported Outcomes

Participant satisfaction, experience with procedure, and psychosocial impact data will be collected via paper questionnaires. These questionnaires have been developed and modified following additional qualitative research based on questions used in previous CoolSculpting studies. The questionnaires include the CSQ-Midsection (Section 10.6), CSQ-Overall (Section 10.7), CSQ-Upper Arms (Section 10.10), CSQ-Inner Thighs (Section 10.9), CSQ-Outer Thighs (Section 10.8), CSQ-Fat under chin (Section 10.11), CGPQ (Section 10.12), and CPIQ (Section 10.13).

The CSQ-Midsection is a 2-item PRO instrument that measures participant satisfaction with results of CoolSculpting treatment and improvement in fit of clothing. CSQ-Overall and the CSQ specific for body area are 1-item PRO instruments that measure participant satisfaction with results of treatment when considering all body areas treated and individual body area, respectively. The CGPQ is a 5-item PRO instrument that assesses participant experience with the CoolSculpting treatment procedure. The questionnaire assesses participant comfort with the

treatment, likelihood of having another fat reduction procedure on a different part of the body, likelihood of recommending the procedure to a friend, and satisfaction with length of time to complete the procedure and achieve visible results. The CPIQ is a 5-item PRO instrument that assesses the psychosocial impact of CoolSculpting treatment, including self-confidence, feeling unhappy, feeling anxious, feeling bothered, and avoiding certain places or situations.

An additional participant question (Participant Evaluation of Noticeable Improvement) will be administered 4 weeks after the first treatment session to assess whether participant starts to observe noticeable improvement with CoolSculpting Elite on the treated body areas at this earlier timepoint (Section 10.14).

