### **8.2.1. Pain Assessment Score**

At Visits 2 and 6 (treatment session 1 and 2 visits), participant pain will be assessed 10 minutes after starting the cooling treatment using a standard scale of 0 to 10, 0 being no pain and 10 being the worst pain imaginable during the treatment cycle. If the pain score worsens during the treatment, this will also be recorded. If discomfort is intolerable, the treatment will be discontinued until the participant is comfortable and treatment, at the discretion of the investigator, can be resumed. Discomfort that results in either a temporary or permanent cessation of the treatment is to be documented as an AE (for additional detail, see Table 2-1 [guidance for anticipated device effects] and Section 8.3 [AEs]).

At Visits 3, 4, 5, 6, 7, and 8, 9 (all other study visits), participant pain will be assessed using a standard scale of 0 to 10, 0 being no pain and 10 being the worst pain imaginable.

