### 4.0 Analysis Populations

The following population sets will be used for the statistical analyses.

The Enrolled Population will consist of all participants who signed the informed consent.

The Safety Population will consist of all enrolled participants who received at least one cryolipolysis treatment cycle (started or completed).

The Evaluable Population 1 will consist of all participants who completed the cryolipolysis treatment plan to the midsection and completed the CSQ-Midsection Item 1 at 12 weeks after the final treatment measured at Visit 8 (Week 12) for participants who receive 1 treatment session, or at Visit 9 (Week 20) for participants who receive 2 treatment sessions, or at 12 weeks +14 days post treatment session 2 for participants who had their treatment session 2 rescheduled because of the CoolSculpting® Elite treatment hold in the US on / after 24th August 2021, and do not have any significant protocol deviation or violation.

The Evaluable Population 2 will consist of all participants who completed the cryolipolysis treatment plan for any other body areas (Upper Arms, Inner Thighs, Outer

Thighs and Submental Area) whether midsection treatment is completed or not, and do not have any significant protocol deviation or violation .

The Evaluable Population 3 will consist of all participants who completed the cryolipolysis treatment plan for any body areas (Midsection, Upper Arms, Inner Thighs, Outer Thighs and Submental Area) and do not have any significant protocol deviation or violation.

The Evaluable Population 4 will consist of all participants who completed the cryolipolysis treatment plan to the midsection and one or more additional body areas (Upper Arms, Inner Thighs, Outer Thighs and Submental Area) and do not have any significant protocol deviation or violation.

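### The CGPQ comfort and recommendation results leave out anyone who permanently stops the midsection plan for discomfort, even if that participant answers the questionnaire

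*SAP*

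**What the plan says.** Protocol 8.1.1 describes the instrument: "The CGPQ is a 5-item PRO instrument that assesses participant experience with the CoolSculpting treatment procedure". It continues: "The questionnaire assesses participant comfort with the" treatment. The other items cover whether the participant would have a different body part treated, would recommend the procedure, and was satisfied with the time taken by the procedure and by the results.

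SAP 9.5.2 reports the response categories of all CGPQ items at the 12-week visit after final treatment. It says that they "will be summarized for the Evaluable Population 1 and Evaluable Population 4". SAP 4.0 defines these sets:

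- Population 1 is "all participants who completed the cryolipolysis treatment plan to the midsection and completed the CSQ-Midsection Item 1 at 12 weeks after the final treatment", with no significant deviation or violation.
- Population 4 is those who "completed the cryolipolysis treatment plan to the midsection and one or more additional body areas", again with no significant deviation or violation.

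The protocol expects some treatments to stop for discomfort. Section 7.1 says that "study intervention may be discontinued due to significant discomfort". Section 8.2.1 says that, for intolerable discomfort, "the treatment will be discontinued until the participant is comfortable and treatment, at the discretion of the investigator, can be resumed". The same section allows for a stop that is not resumed: "Discomfort that results in either a temporary or permanent cessation of the treatment is to be documented as an AE".

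**The concern.** Membership of both analysis sets depends on finishing the midsection plan, and discomfort is a foreseen reason for not finishing it. For the comfort item, the analysis set is thus partly selected on the quantity being measured. Willingness to recommend is likely to be affected in the same direction.

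The excluded answers may well exist. A participant who stops treatment but stays in the study can complete the CGPQ at Visit 8 or 9, and Protocol 7.2 encourages those who withdraw to complete the final evaluations. SAP 9.2 allows no imputation, and no CGPQ summary in the Safety Population is visible.

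Treatment experience is part of the rationale in Protocol 2.1, which also aims to inform providers and patients about expected outcomes. A comfort percentage from plan completers could be read as the experience of everyone treated.

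**Working it through.** **Who is excluded.** Setting SAP 4.0 and 9.5.2 beside Protocol 7.1 and 8.2.1:

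| Participant | Population 1 | Population 4 |
|---|---|---|
| Pauses for discomfort, resumes and completes the midsection | eligible | eligible if another area is also completed |
| Completes the midsection, stops another area | eligible | eligible only if a further area is completed |
| Permanently stops the midsection plan | out | out |
| Declines the optional second midsection session | unclear | unclear |

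The last row is unclear because neither document defines a completed treatment plan, and Protocol Table 6-1 sets the midsection minimum at one session.

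Protocol 9.3 is wider in one respect. For effectiveness endpoints other than the primary, it keeps treated participants who completed another body area, regardless of midsection completion. SAP 4.0 carries this into Populations 2 and 3, but SAP 9.5.2 uses neither for the CGPQ.

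**The plan's own figure.** No figure is given for the CGPQ. The 96 used below is the planned number completing the primary assessment (SAP 2.4). The Clopper-Pearson 95% interval at 63.9%, with a non-integer count allowed, has width 0.20104 at n = 95 and 0.19996 at n = 96, so 96 is reproduced as the smallest n with width at most 0.2. Attrition of 12% gives 96/0.88 = 109.1, rounded up to 110.

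**Illustration.** All inputs except 96 and 110 are assumptions. Let x be the comfortable completers out of 96, k the excluded stoppers who answer, and m the comfortable stoppers among them.

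- Planned result: x/96.
- Result with stoppers included: (x + m)/(96 + k).
- With m = 0, the difference is (x/96) × k/(96 + k).

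| Completers comfortable | k = 2 | k = 5 | k = 14 |
|---|---|---|---|
| 67/96 = 69.8% | 68.4% | 66.3% | 60.9% |
| 77/96 = 80.2% | 78.6% | 76.2% | 70.0% |
| 86/96 = 89.6% | 87.8% | 85.1% | 78.2% |

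In the middle row, 77/98 = 78.6% and 77/101 = 76.2%, shifts of 1.6 and 4.0 points. The exact 95% interval is 70.8% to 87.6% for 77/96 and 66.7% to 84.1% for 77/101. The column k = 14 is an extreme: it treats all 110 − 96 = 14 planned losses as discomfort stops who answered and were not comfortable.

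The shift falls if some stoppers were comfortable: with 2 of 5 comfortable, 79/101 = 78.2%, a shift of 2.0 points. It also falls if only some answer: with 3 of 5 answering and none comfortable, 77/99 = 77.8%, a shift of 2.4 points.

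**The case against.** The other side has a good deal in its favour.

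- **Narrow exclusion.** A reader might infer that everyone who stopped for discomfort is removed by definition. The documents do not support that. Protocol 8.2.1 provides for resuming, each session's plan may be spread over 7 days, and Population 1 concerns the midsection only. This stands and limits the point to permanent midsection stops.
- **Discomfort is reported elsewhere.** A reader might also infer that discomfort among stoppers is hidden. It is not. SAP 6.0 tabulates interrupted and discontinued treatments with reason in the Safety Population. Discomfort that halts treatment is an adverse event. SAP 10.5.1 summarises pain at 10 minutes, worst pain during the cycle and pain at later visits. This stands, but none of it changes the CGPQ percentages.
- **The SAP follows the protocol.** Protocol 9.4.1 bases effectiveness analyses on the evaluable population. That is true in general, but the sets chosen for the CGPQ are narrower than Protocol 9.3 for participants who complete only a non-midsection area.
- **Other items.** Satisfaction with procedure time and with time to visible results is naturally asked of completers. This is fair; the argument is strongest for comfort and recommendation.
- **Early exits.** Protocol 7.2 already encourages final evaluations at withdrawal. Pooling those answers would break the schedule's requirement of at least 12 weeks since final treatment. This stands, and the fix keeps them apart.
- **Redaction.** Parts of SAP 9.5 are blacked out, so a further CGPQ listing or analysis cannot be ruled out. The CGPQ paragraph itself is intact.

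**Conclusion.** The point holds for participants who permanently stop the midsection plan for discomfort: they are in neither CGPQ analysis set, whether or not they answer.

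It would go too far to say that the comfort result is biased upward as a matter of fact. That needs at least one such participant with a response, and stoppers who were less comfortable than completers. Both are plausible, but the documents establish neither. They give no comfort rate, stopping rate or response rate, so the size cannot be computed. Under the assumptions shown (96 completers, 80.2% comfortable, no stopper comfortable), the shift is 1.6 points for 2 stoppers and 4.0 points for 5, well inside the width of the interval.

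The endpoint is exploratory and descriptive, and no hypothesis is tested. The effect is on how the CGPQ result is read, not on the primary conclusion. Priority is low.

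**What to change.** In SAP 9.5.2:

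1. Summarise each CGPQ item for all Safety Population participants with a CGPQ response at the 12-week post-final-treatment visit.
2. Keep the Evaluable Population 1 and 4 summaries as supplementary.
3. Show beside the new summary the number of participants who stopped treatment for discomfort, and how many of them answered. SAP 6.0 already tabulates stopped treatments with reason; its count is of treatments, so a participant count should be derived from the same data.
4. Present any early-exit CGPQ responses separately, because their timing differs.

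A line in SAP 4.0 saying what counts as a completed treatment plan would also settle who is excluded from the supplementary summaries.

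The cost is SAP wording, one extra table and a possibly slightly less favourable figure. No new data collection is needed. Stoppers who do not answer remain missing, which is why their number should be shown. Label: cheap improvement.
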